12.9.1 Case Report Forms

All required data for this study will be collected via cloud-based electronic data capture (EDC) system and entered in electronic Case Report Forms (eCRFs).

All data collected during the study will be de-identified. For this purpose, a unique study identifier will be assigned to each study subject. All information recorded on the electronic Case Report form (eCRF) about the subject will be recorded including the study identifier. The database will contain only the study identifier to identify the subject. The code with subject name and study number will be maintained by the Principal Investigator in a secured location. Subject names will not be released to Shockwave Medical at any stage of the study.

12.9.2 Transmission of Data

Required data will be recorded on the appropriate electronic Case Report Forms at the time of or as soon as possible after the subject visit. The eCRF and any requested supporting source documents (including medical imaging files and source information associated with adverse events) must be sent to Shockwave Medical (if applicable to local site regulations) and/or verified/retrieved from the Investigator during monitoring visits. Data sent to Shockwave Medical will be de-identified and done so utilizing a secure web-based system.

12.9.3 Data Queries

Any data discrepancies identified during data review or a monitoring visit will be queried by Shockwave Medical or its designee and must be resolved by the investigational site staff and Investigator in a timely manner.

Data audits may be performed by Shockwave Medical or its designee for quality assurance of data handling. Any discrepancies will be queried by Shockwave Medical or its designee and must be resolved by the investigational site staff and Investigator in a timely manner, particularly during those times data is being prepared for CEC safety reviews and reports required by the regulatory authorities.

	No.: CP 67398	REV. C
	TITLE: FORWARD PAD IDE Study Protocol	
	CLASS: CLINICAL PROTOCOL	PAGE 50 OF 65

12.9.4 Data Retention

Shockwave Medical will retain all study data received for a period of two (2) years after the investigation is completed or terminated, or two (2) years after the records are no longer required to support the application to market the device (whichever date is later), or longer if required by applicable local regulations. The data will be retained in a secure, password protected database under the custodianship of the Sponsor and stored in the United States of America.

 SHOCKWAVE <small>MEDICAL INC</small>	No.: CP 67398	REV. C
	TITLE: FORWARD PAD IDE Study Protocol	
	CLASS: CLINICAL PROTOCOL	PAGE 51 OF 65

13.0 STUDY COMMITTEES

13.1 Clinical Events Committee (CEC)

To meet the ethical responsibilities and standards for research subjects, an independent Clinical Events Committee shall serve as forum for adjudication of certain pre-specified clinical event types, including SAEs, as described in the CEC charter.

The CEC will be managed [REDACTED]

In order to enhance objectivity and reduce the potential for bias, the CEC shall be independent of the Study Sponsor as well as the study investigators.

The CEC is made up of clinicians with pertinent expertise who are not participants in the study and who do not have any other real or potential conflicts of interest. Members have expertise in peripheral endovascular procedures, are experienced in the conduct of controlled clinical trials and have knowledge of bioethics and integrity related to the duties and responsibilities to be performed.

The CEC is charged with the development of specific criteria used for the categorization of adverse events and clinical endpoints in the study. Criteria will be established for selected complications and clinical events. Events to be adjudicated include death, MAEs, revascularizations, and amputations. The CEC will also adjudicate relationship to the study device and study procedure according to the following classifications: definitely related, probably related, possibly related, unlikely related and not related.

At the onset of the study, the CEC will establish explicit rules outlining the minimum amount of data required and the algorithm followed in order to classify an event. The methodology for performing these responsibilities shall be developed and outlined in the CEC Charter. Operational provisions shall be established to minimize potential bias (i.e., CEC members shall be blinded to the clinical site to the extent possible during adverse event review and adjudication). The methodology for performing these responsibilities shall be developed and outlined in the CEC Charter. In addition, the CEC Charter will include the number of members, responsibilities, CEC meeting procedures, and meeting frequency.

13.2 Independent Data and Safety Monitor (DSM)

An independent Data and Safety Monitor (DSM) will be responsible for reviewing study data, monitoring for excessive occurrence of adverse events and making recommendations to Shockwave Medical regarding safety issues and risks to research participants as well as the continuing validity and scientific merit of the study. The DSM will make recommendations including (but not limited to) modification of the protocol, continuation/discontinuation of enrollment, and/or temporary suspension of enrollment in the trial. The DSM will be a physician with required training, experience and expertise in the field of peripheral endovascular procedures and in the conduct of clinical trials.

 SHOCKWAVE <small>MEDICAL INC</small>	No.: CP 67398	REV. C
	TITLE: FORWARD PAD IDE Study Protocol	
	CLASS: CLINICAL PROTOCOL	PAGE 52 OF 65

The independent DSM will conduct reviews of safety data in accordance with the protocol, local regulations where applicable, ICH E6: Good Clinical Practice (GCP) guidelines, and ISO14155:2020. At regular intervals during the course of the study, the DSM shall:

- Evaluate all adverse events with regard to interim results of the study for evidence of undue risk to research subjects and/or safety concerns.
- Provide recommendations regarding continuation/discontinuation of enrollment, and/or temporary suspension of enrollment due to safety concerns.
- Evaluate study progress with projections of recruitment and timelines for study milestones. This also includes evaluation of any significant trends of performance that may influence the safety or conduct of the study.
- Advise the Sponsor and other responsible parties on potential protocol-related concerns regarding procedures, definitions or endpoints, allowing timely notification of regulatory authority for protocol revisions.

In addition to regularly scheduled data reviews, the DSM will be notified immediately if any of the following events occur: any in-hospital death associated with the index procedure, any investigational device malfunction contributing to a serious adverse event, or failure to retrieve the investigational device.

 SHOCKWAVE <small>MEDICAL INC</small>	No.: CP 67398	REV. C
	TITLE: FORWARD PAD IDE Study Protocol	
	CLASS: CLINICAL PROTOCOL	PAGE 53 OF 65

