5.1 Safety Endpoints

The safety endpoints for this study include:

- **PRIMARY: Major Adverse Events (MAE)** at 30 days defined as a composite of:
 - Cardiovascular death
 - Clinically-driven target lesion revascularization (CD-TLR)
 - Unplanned target limb major amputation (above the ankle)
- **MAE** at 6 and 12 months (as a composite and individual components)
- **Serious angiographic complications** defined as flow-limiting dissection (\geq grade D), perforation, distal embolization, or acute vessel closure as assessed by the angiographic core lab.

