7.4 Schedule of Events and Evaluations

Table 1 lists the schedule of events and evaluations required for the study.

 SHOCKWAVE <small>MEDICAL INC</small>	No.: CP 67398	REV. C
	TITLE: FORWARD PAD IDE Study Protocol	
	CLASS: CLINICAL PROTOCOL	PAGE 24 OF 65

Table 1. Schedule of Events and Evaluations

Assessment	Screening / Baseline	Enrollment and Procedure	Discharge ¹	30 Days (-7/+14 days)	6 Month (180±30 days)	12 Month (360±30 days)
Eligibility	✓					
Informed Consent ²	✓					
Medical History	✓					
Physical Exam	✓			✓	✓	✓
eGFR	✓					
Pregnancy Test	✓ ³					
Medications	✓		✓	✓	✓	✓
ABI or TBI	✓ ⁴			✓	✓	✓
Rutherford Category	✓			✓	✓	✓
Angiogram or IVUS		✓				
DUS						✓
Adverse Events		✓	✓	✓	✓	✓
ABI = ankle-brachial index; TBI = toe-brachial index 1. Within 12-24 hours post procedure or prior to hospital discharge, whichever occurs first 2. Consent to be obtained within 30 days prior to procedure. 3. Within seven (7) days of the procedure for women of child-bearing age. 4. Within 60 days prior to procedure.						

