7.8 Follow-Up

7.8.1 Discharge or Within 12-24 Hours Post-Procedure

The following assessments and procedures will be performed within **12-24 hours** post procedure or prior to hospital discharge, whichever occurs first:

- Review of anticoagulation/antiplatelet medications
- Adverse event assessment

7.8.2 30-Day Follow-Up

The following evaluations will be performed at **30 days** (-7/+14 days) post procedure:

- Physical examination
 - Vital signs
- ABI or TBI of target limb (at rest; keep consistent with screening)
- Rutherford Category of target limb
- Review of anticoagulation/antiplatelet medications
- Adverse event assessment

Note: If treatment of two target lesions is planned across both limbs, the Rutherford Category and ABI/TBI for each limb must be assessed. If ABI/TBI cannot be assessed due to non-compressible vessels, this should be documented.

7.8.3 6-Month Follow-Up

The following evaluations will be performed at **6 months** (180 +/-30 days) post procedure:

- Physical examination
 - Vital signs
- ABI or TBI of target limb (at rest; keep consistent with screening)

 SHOCKWAVE <small>MEDICAL INC</small>	No.: CP 67398	REV. C
	TITLE: FORWARD PAD IDE Study Protocol	
	CLASS: CLINICAL PROTOCOL	PAGE 31 OF 65

- Rutherford Category of target limb
- Review of anticoagulation/antiplatelet medications
- Adverse event assessment

Note: If treatment of two target lesions is planned across both limbs, the Rutherford Category and ABI/TBI for each limb must be assessed. If ABI/TBI cannot be assessed due to non-compressible vessels, this should be documented.

7.8.4 12-Month Follow-Up

The following evaluations will be performed at **12 months** (360 +/-30 days) post procedure:

- Physical examination
 - Vital signs
- ABI or TBI of target limb (at rest; keep consistent with screening)
- Rutherford Category of target limb
- Review of anticoagulation/antiplatelet medications
- Adverse event assessment
- Duplex ultrasound (DUS)

Note: If treatment of two target lesions is planned across both limbs, the Rutherford Category and ABI/TBI for each limb must be assessed. If ABI/TBI cannot be assessed due to non-compressible vessels, this should be documented.

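### Unless a device malfunction contributed, Protocol 13.2 gives the independent monitor no immediate notice of a death after discharge or of a major amputation

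*Protocol*

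**What the plan says.** Protocol 13.2 sets up two routes to the DSM. The scheduled route covers all adverse events: "At regular intervals during the course of the study, the DSM shall" evaluate them and make recommendations on enrollment. No interval is given in time or in number of subjects.

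The immediate route is an addition: "In addition to regularly scheduled data reviews, the DSM will be notified immediately if any of the following events occur". The list has three entries: "any in-hospital death associated with the index procedure", and then "any investigational device malfunction contributing to a serious adverse event, or failure to retrieve the investigational device".

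The primary safety endpoint in Protocol 5.1 is "Major Adverse Events (MAE) at 30 days defined as a composite of" cardiovascular death, clinically-driven target lesion revascularization (CD-TLR) and unplanned major amputation of the target limb. SAP 4.1 has the same three components. Protocol 9.2.1 lists all-cause death and target limb revascularization instead. That is a separate inconsistency, and this point stands under either version.

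Protocol 10.4.2 has sites report serious adverse events to the sponsor within 2 business days of learning of them. Protocol 12.5 obliges the sponsor to suspend the study on suspicion of unacceptable risk. Neither section mentions the DSM.

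**The concern.** The DSM is the independent role charged with watching for an excess of adverse events and advising whether enrollment should continue. The immediate list does not follow the safety question that the study asks. It covers a death only if it occurs in hospital and is associated with the procedure, and it never names amputation. The text does not say who decides on association or by what standard. Relatedness is assessed by the investigator (10.2) and adjudicated by the Clinical Events Committee (CEC) (13.1), so the judgement may be made before the monitor hears of the death.

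What is at stake is time. Subjects can go on being treated with an investigational device between a death or limb loss and the first look by the independent monitor. The supporting experience quoted in Protocol 3.1.3 is 11 subjects followed for 30 days. Protocol 8.1 accepts that there may be no additional benefit from taking part, because commercial lithotripsy is available.

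**Working it through.** **1. Events set against the immediate list in 13.2.**

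| Event within 30 days | Immediate DSM notice? |
|---|---|
| Death in hospital, associated with the procedure | Yes |
| Death in hospital, not deemed associated | No |
| Death after discharge | No |
| Unplanned major amputation of target limb, in or out of hospital | No |
| CD-TLR | No |
| Any of these, as a serious adverse event, where a device malfunction contributed | Yes, at any time and in any place |

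**2. Share of the 30-day window outside the in-hospital trigger.** Let d be the length of stay in days; the share is (30 − d)/30. The protocol gives no d. The nearest text is the discharge assessment in Table 1, timed "Within 12-24 hours post procedure or prior to hospital discharge, whichever occurs first". That fixes when an assessment is made, not when the subject goes home. So d is an assumption:

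- d = 1: 29/30 = 96.7%
- d = 2: 28/30 = 93.3%
- d = 3: 27/30 = 90.0%
- d = 7: 23/30 = 76.7%

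This takes in-hospital to mean the index stay. It is a share of days, not of events, because the documents do not say when in the window events are expected. For amputation without a malfunction the share is 100% whatever d is.

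**3. Subjects enrolled while an event waits.** Protocol 6.2 and 6.3 give up to 75 subjects over about 12 months: 75/12 = 6.25 per month. With an assumed review interval of m months, an event just after a review waits while up to 6.25 × m subjects are enrolled: about 6 for m = 1, 19 for m = 3 (18.75) and 38 for m = 6 (37.5). The interval is my assumption, since none is stated.

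**4. The plan's own safety figures, for context.** With 90 subjects, a goal of 11.2% and one-sided α = 0.025 (Protocol 9.3), the largest allowable count is 4: P(X ≤ 4 | 90, 0.112) = 0.0218. Power is P(X ≤ 4 | 90, 0.02) = 96.5%, as stated. The expected count is 90 × 0.02 = 1.8. None of this moves with the time at which the DSM is told.

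**The case against.** The case for leaving 13.2 alone has real content.

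- **The device triggers.** A reader might infer that the monitor hears at once of nothing but certain in-hospital deaths. That is wrong. The two device triggers are not limited to the hospital stay, so a death at home or an amputation to which a malfunction contributed is notified immediately.
- **The 24-hour figure.** A reader might infer that the death trigger covers one day in thirty. The documents do not support this as a fact, because the 12–24 hour figure times an assessment. Nor does 13.2 say that the hospital stay must be the index one, so an associated death on readmission is arguably covered. SAP Appendix A counts discharge-day events as in-hospital, but that is a reporting convention.
- **Other safeguards.** Sites report within 2 business days, the sponsor must act on unacceptable risk, the independent CEC adjudicates deaths, amputations and relatedness, and the DSM eventually sees every adverse event. No event is lost.
- **The success rule.** It is tempting to measure the gap by the 4-in-90 limit. That rule governs the final pooled analysis over two studies and is unaffected by notification timing.
- **No contradiction.** Nothing in the documents requires immediate triggers to mirror the endpoint.

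All of this narrows the point. It does not close it: none of these provisions sends a death or amputation without a malfunction to the DSM before its next scheduled review.

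**Conclusion.** The gap is real but limited. It is a gap in routing to the independent monitor, not a failure of safety reporting or a flaw in the analysis. Without a contributing malfunction, post-discharge deaths, in-hospital deaths not deemed associated, and all major amputations of the target limb wait for a review of unstated frequency.

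For deaths, the uncovered part of the window is about 97% to 77% for assumed stays of 1 to 7 days. For amputations it is the whole window. The number of subjects treated in the meantime depends on a review interval that the plan does not give.

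This is a cheap improvement worth making. It should not be read as evidence that events go unreported or that the study's conclusions are at risk.

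**What to change.** In Protocol 13.2, replace the death trigger with any death within 30 days of the index procedure, wherever it occurs and whatever its attributed cause. Add any unplanned major amputation of the target limb within 30 days, the window already used in the definition of unplanned amputation in 15.1. Keep both device triggers. State that the sponsor forwards to the DSM the serious adverse event report it already receives under 10.4.2.

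Two details of drafting:

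- An associated in-hospital death after day 30 is covered now and would drop out of a 30-day rule. Retaining the present wording for that case avoids the loss.
- Stating the scheduled review interval in the same section would let a reader judge the wait for everything else, including CD-TLR, which this change leaves on the scheduled route.

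The change belongs in 13.2 itself, since the documents mention a charter for the CEC but none for the DSM.

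The cost is a small number of extra forwarded reports, some of them on unrelated deaths. The documents give no rate for this set of events. The 2.0% planning rate (1.5 in 75 subjects) cannot stand in for it, because that rate includes CD-TLR and, under Protocol 5.1, excludes non-cardiovascular deaths. The change shortens only the step from sponsor to monitor. It cannot speed up a site's first knowledge of an event that happens at home.

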14.0 ETHICAL and REGULATORY CONSIDERATIONS

14.1 Role of Shockwave Medical

As the Study Sponsor of this clinical study, Shockwave Medical has the overall responsibility for conduct of the study, including assurance that the study will be conducted according to ICH Good Clinical Practices (GCP), 21 CFR 812, 820, 50, 54, and 56, Declaration of Helsinki, applicable IRB requirements, as well as any ISO 14155 and/or national requirements. In this study, Shockwave Medical will have certain direct responsibilities and may delegate other responsibilities to qualified consultants and/or contract research organizations. The specific federal regulations, international standards, and/or guidelines required to be followed should be outlined within the protocol. Sponsor will provide insurance for this study.

This protocol and any amendments will be submitted to each site's IRB for formal approval of the study. All subjects considered for this study will be provided a consent form describing this study and providing sufficient information for them to make an informed decision about their participation.

14.2 Subject Confidentiality

As per the Data Management Section 12.9, subject confidentiality will be maintained throughout the clinical study. A unique subject identification code will be assigned and used to allow identification of all data reported for each subject.

Study data may be made available to third parties such as regulatory or auditing agencies (e.g., in the case of an audit) provided the data are treated confidentially and that the subject's privacy is guaranteed. The identity of a subject will never be disclosed in the event that study data are published. Data will not be provided to third party agencies that are not associated with the commercial or research operations of the Sponsor.

 SHOCKWAVE <small>MEDICAL INC</small>	No.: CP 67398	REV. C
	TITLE: FORWARD PAD IDE Study Protocol	
	CLASS: CLINICAL PROTOCOL	PAGE 54 OF 65

15.0 DEFINITIONS and ABBREVIATIONS

15.1 Study Definitions

Abrupt or Acute Closure: Angiographic documentation of significantly reduced flow due to mechanical dissection, thrombus, or severe vessel spasm in the treatment area.

Acute Limb Ischemia: A sudden decrease in limb perfusion that causes a potential threat to limb viability (manifested by ischemic rest pain, ischemic ulcers, and/or gangrene) in patients who present within two weeks of the acute event.

Adverse Device Effect (ADE): Adverse event related to the use of an investigational medical device.

Note: This definition includes adverse events resulting from insufficient or inadequate instructions for use, deployment, implantation, installation, or operation, or any malfunction of the investigational medical device.

Note: This definition includes any event resulting from use error or from intentional misuse of the investigational medical device.

Note: This includes “comparator” if the comparator is a medical device.

Adverse Event (AE): Untoward medical occurrence, unintended disease or injury, or untoward clinical signs (including abnormal laboratory findings) in subjects, users or other persons, whether or not related to the investigational medical device and whether anticipated or unanticipated.

Note: This definition includes events related to the investigational medical device or the comparator.

Note: This definition includes events related to the procedures involved.

Note: For users or other persons, this definition is restricted to events related to the use of investigational medical devices or comparators.

Amputation (major): Any requirement for amputation above the ankle.

Amputation (minor): Any requirement for amputation below the ankle.

Amputation, Unplanned: An amputation associated with the target limb that occurs between the index procedure and 30 days that was not previously planned as part of the overall treatment strategy.

Ankle-Brachial Index (ABI): The ratio of systolic blood pressure measured at the ankle to systolic blood pressure measured at the brachial artery.

Calcification Classification (PARC): Calcification will be assessed by the angiographic core lab according to the Peripheral Academic Research Consortium (PARC) definition [22].

PARC Degree of Lesion Calcification

Focal	Degree of lesion calcification
Mild	<180° and greater than one-half of the total lesion length
Moderate	≥180° (both sides of vessel at same location) and less than one-half of the total lesion length
Severe	>180° (both sides of the vessel at the same location) and greater than one-half of the total lesion length

Clinical Events Committee (CEC): Committee responsible for establishing and implementing decision rules, definitions for the adjudication of clinical events using the data collected in the study, and for providing unbiased adjudication of clinical events.

Clinically Relevant Target Lesion Occlusion: Clinically relevant restenosis defined as the presence of a 50% or greater narrowing accompanied by a judgement of clinical relevance. Clinical relevance adjudicated by independent CEC based on worsening of Rutherford score, non-healing of wounds, ABI drop of ≥0.15, TBI drop of ≥0.10, each as compared to post-procedural outcomes, or absolute toe pressure ≤30 mmHg.

Closure, Abrupt: Occurrence of new (during the index procedure), persistent slow, reduced, or loss of flow within the target vessel that requires intervention other than the index or adjunct treatment. Abrupt closure may also be referred to as acute occlusion if there is a total loss of flow.

Closure, Subacute: Target lesion site occlusion that occurs after the index procedure is completed (e.g., the subject has left the treatment area) and within 30 days of procedure.

Critical Limb Ischemia: Clinical manifestation of peripheral arterial disease characterized by Rutherford Clinical Scale Category of 2-6. (For the purposes of this study, only subjects with Rutherford Clinical Scale Category of 2, 3, 4, and 5 are eligible for enrollment).

Data and Safety Monitor (DSM): Data and Safety Monitor will be responsible for reviewing study data, monitoring for excessive occurrence of adverse events and making recommendations to Shockwave Medical regarding safety issues and risks to research participants as well as the continuing validity and scientific merit of the study.

Death: (divided into 2 categories)

Cardiac death is death due to any of the following:

1. Acute myocardial infarction
2. Cardiac perforation/periocardial tamponade
3. Arrhythmia or conduction abnormality
4. Stroke within 30 days of the procedure or stroke suspected of being related to the procedure
5. Death due to complication of the procedure, including bleeding, vascular repair, transfusion reaction, or bypass surgery

 SHOCKWAVE <small>MEDICAL INC</small>	No.: CP 67398	REV. C
	TITLE: FORWARD PAD IDE Study Protocol	
	CLASS: CLINICAL PROTOCOL	PAGE 56 OF 65

6. Any death for which a cardiac cause cannot be excluded

Non-cardiac death is a death not due to cardiac causes (as defined immediately above).

Device Deficiency: Inadequacy of a medical device with respect to its identity, quality, durability, reliability, usability, safety or performance.

Note: Device deficiencies include malfunctions, use errors, and inadequacy in the information supplied by the manufacturer including labelling.

Note: This definition includes device deficiencies related to the investigational medical device or the comparator.

Device Malfunction: A malfunction of a device is an unexpected change to the device that is contradictory to the Instructions for Use and may or may not affect device performance.

Dissection: Disruption of an arterial wall resulting in separation of the intimal layer. May or may not be flow limiting.

Dissection Classifications (National Heart, Lung and Blood Institute – NHLBI)

Type A: Minor radiolucent areas within the lumen without impairment of flow or persistent dye staining after contrast runoff.

Type B: Luminal flap that is radiolucent and runs parallel to the vessel wall with contrast injection but without impairment of flow or persistent dye staining after contrast runoff.

Type C: Contrast appears outside of the vessel lumen as an “extraluminal cap”, the staining appears even after contrast clears off the lumen.

Type D: Spiral radiolucent luminal filling defects, often persistent staining after contrast clears from the vessel.

Type E: New and persistent filling defects in the vessel lumen.

Type F: Lesions that progress to impaired flow or total occlusion.

Embolization, Distal: Any distal emboli confirmed by imaging considered to be related to the target lesion(s).

Embolization, Symptomatic: Clinical signs or symptoms of distal emboli detected in the treated limb distal to the treated lesion after the index procedure **or** noted angiographically and requiring mechanical or pharmacologic means to improve flow. This includes new abrupt occlusions or filling defects.

Intravascular Lithotripsy (IVL): Shockwave Medical’s proprietary balloon angioplasty catheter including lithotripsy technology that creates pulsatile mechanical energy for disrupting calcified vascular plaque.

Limb Ischemia: Deficient supply of oxygenated blood to the tissues in the limbs that is due to obstruction of the inflow of arterial blood characterized by pain and/or discoloration of the limb.

Lithotripsy: A medical procedure for disrupting calculus in the body.

 SHOCKWAVE <small>MEDICAL INC</small>	No.: CP 67398	REV. C
	TITLE: FORWARD PAD IDE Study Protocol	
	CLASS: CLINICAL PROTOCOL	PAGE 57 OF 65

Luminal Patency: Post-procedure residual stenosis <50% as determined by investigator visual assessment or quantitative analysis of the end of procedure angiogram.

Major Adverse Event (MAE): For the purposes of this study, the definition of Major Adverse Event(s) includes:

- cardiovascular death
- target lesion revascularization
- Unplanned target limb major amputation (above the ankle)

Perforation: Puncture of an arterial wall.

Restenosis: Reoccurrence of narrowing or blockage of target lesion.

Rutherford Classification of Critical Limb Ischemia: Clinical staging system for describing PAD. It includes 7 categories:

Grade	Category	Clinical Description
0	0	Asymptomatic
I	1	Mild claudication
	2	Moderate claudication
	3	Severe claudication
II	4	Ischemic rest pain
	5	Ischemic ulceration not exceeding ulcer of the digits of the foot
IV	6	Severe ischemic ulcers or frank gangrene

(ACC/AHA/SCAI/SIR/SVM 2018 Appropriate Use Criteria for Peripheral Artery Intervention – Bailey et al. 2019)

Serious Adverse Device Effect (SADE): Adverse device effect that has resulted in any of the consequences characteristic of a serious adverse even.

Serious Adverse Event (SAE): Adverse event that led to any of the following:

 SHOCKWAVE <small>MEDICAL INC</small>	No.: CP 67398	REV. C
	TITLE: FORWARD PAD IDE Study Protocol	
	CLASS: CLINICAL PROTOCOL	PAGE 58 OF 65

- death,
- serious deterioration in the health of the subject, user, or other persons as defined by one or more of the following:
 - a life-threatening illness or injury, or
 - a permanent impairment of a body structure or a body function including chronic diseases, or
 - in-patient or prolonged hospitalization, or
 - medical or surgical intervention to prevent life-threatening illness or injury, or permanent impairment to body structure or a body function,
 - fetal distress, fetal death, a congenital abnormality, or birth defect including physical or mental impairment.

Note: Planned hospitalization for a pre-existing condition, or a procedure required by the CIP, without serious deterioration in health, is not considered a serious adverse event.

Target Lesion Revascularization, Clinically-driven (TLR): A target lesion revascularization performed due to target lesion diameter stenosis $\geq 50\%$ and either evidence of clinical or functional ischemia (e.g., recurrent/progressive life-limiting intermittent claudication, claudication unresponsive to medical therapy, CLI) or recurrence of the clinical syndrome for which the initial procedure was performed. Clinically-driven target lesion revascularization (CD-TLR) occurs in the absence of protocol directed surveillance ultrasound or angiography.

Target Vessel Revascularization, Clinically-driven (TVR), non-TLR: A target vessel revascularization performed due to non-target lesion diameter stenosis $\geq 50\%$ and either evidence of clinical or functional ischemia (e.g., recurrent/progressive life-limiting intermittent claudication, claudication unresponsive to medical therapy, CLI) or recurrence of the clinical syndrome for which the initial procedure was performed. Clinically driven target vessel revascularization occurs in the absence of protocol directed surveillance ultrasound or angiography.

Total Occlusion A 100% stenotic lesion as documented by angiographic absence of flow.

Toe Brachial Index (TBI): The ratio of systolic blood pressure measured at the toe to systolic blood pressure measured at the brachial artery.

Unanticipated Serious Adverse Device Effect (USADE): Serious adverse device effect which by its nature, incidence, severity or outcome has not been identified in the current risk assessment.

Note: Anticipated serious adverse device effect (ASADE) is an effect which by its nature, incidence, severity or outcome has been identified in the risk assessment.

Wound: Foot ulcer or gangrene. After debridement and/or minor amputation, a wound is characterized as a healed wound when it is completely epithelialized.

